9.2 Safety Event Reporting Procedures

9.2.1 Reporting Procedures for Disease Related Events

Disease-related events are defined in Section [9.1.1](#).

The investigator is responsible for ensuring that all disease related events (serious or non-serious) observed by the investigator or reported by the subject that occur after the first dose of talimogene laherparepvec or pembrolizumab through 30 (+7) days after the last dose of talimogene laherparepvec or pembrolizumab, whichever is later, are reported using the events CRF. Additionally, the investigator is required to report a fatal disease related event on the events CRF as a serious adverse event.

All serious disease-related events will be recorded and reported to the sponsor or designee within 24 hours. The investigator will submit any updated serious disease-related event data to the sponsor within 24 hours of it being available.

Disease-related events assessed by the investigator to be more severe than expected and/or related to the talimogene laherparepvec or pembrolizumab, and determined to be serious must be reported on the events CRF as serious adverse events and recorded and reported per Section [9.2.3](#). The investigator must assign the following attributes to each disease-related event:

- Disease-related event diagnosis or syndrome(s), if known (if not known, signs or symptoms),
- Dates of onset and resolution (if resolved),
- Did the event start prior to first dose of investigational product and other protocol-required therapies,
- Assessment of seriousness,
- Severity (and/or toxicity per protocol),
- Assessment of relatedness to talimogene laherparepvec/placebo and/or pembrolizumab, and/or study-mandated activity and/or procedures,
- Action taken, and
- Outcome of event

CTCAE version 4.03 will be used to grade a disease related event. The grading scale used in this study is described in [Appendix A](#).

*Note: If the event is more severe than expected for the subject's condition or if the investigator believes there is a causal relationship between the investigational

product(s)/study treatment/protocol required therapies and disease worsening, the event should be reported as an adverse event, not a disease-related event.

The investigator is expected to follow reported disease-related events (serious or non-serious) until stabilization or reversibility.

9.2.2 Reporting Procedures for Adverse Events That do not Meet Serious Criteria

The investigator is responsible for ensuring that all adverse events observed by the investigator or reported by the subject that occur after the first dose of talimogene laherparepvec or pembrolizumab through 30 (+7) days after the last dose of talimogene laherparepvec or pembrolizumab, whichever is later, are reported using the applicable CRF (eg, events CRF).

All adverse events that occur after the consent form is signed but before enrollment must be reported by the investigator if they cause the subject to be excluded from the trial, or are the result of a protocol-specified intervention, including but not limited to washout or discontinuation of usual therapy, diet, or a procedure. Refer to Section 9.2.5.1 for management of hepatic events of clinical interest.

The investigator must assign the following attributes to each adverse event:

- adverse event diagnosis or syndrome(s), if known (if not known, signs or symptoms), dates of onset and resolution (if resolved),
- did the event start prior to first dose of investigational product and other protocol-required therapies,
- assessment of seriousness,
- severity (and/or toxicity per protocol),
- assessment of relatedness to talimogene laherparepvec and/or pembrolizumab,
- action taken, and
- outcome of event

The adverse event grading scale used will be the CTCAE version 4.03. The grading scale used in this protocol is described in [Appendix A](#). The investigator must assess whether the adverse event is possibly related to the talimogene laherparepvec and/or pembrolizumab. This relationship is indicated by a “yes” or “no” response to the question: “Is there a reasonable possibility that the event may have been caused by talimogene laherparepvec and/or pembrolizumab”?

The investigator must assess whether the adverse event is possibly related to any study-mandated activity (eg, administration of talimogene laherparepvec and/or procedure [including any screening procedure]). This relationship is indicated by a “yes” or “no” response to the question: “Is there a reasonable possibility that the event may have been caused by a study activity (eg, administration of talimogene laherparepvec, and/or procedure”)?

The investigator is responsible for reviewing laboratory test results and determining whether an abnormal value in an individual study subject represents a clinically significant change from the subject’s baseline values. In general, abnormal laboratory findings without clinical significance (based on the investigator’s judgment) are not to be recorded as adverse events. However, laboratory value changes that require treatment or adjustment in current therapy are considered adverse events. Where applicable, clinical sequelae (not the laboratory abnormality) are to be recorded as the adverse event.

If the severity of an adverse event worsens from the date of onset to the date of resolution, record a single event for each increased level of severity on the events CRF. The Investigator is expected to follow reported adverse events until stabilization or reversibility.

It is not acceptable for the investigator to send photocopies of the subject’s medical records to (sponsor/responsible contact research organization [CRO]) in lieu of completion of the Events CRF page.

9.2.3 Reporting Procedures for Serious Adverse Events

The investigator is responsible for ensuring that all serious adverse events, follow up to a serious adverse event, including death due to any cause, observed by the investigator or reported by the subject that occur after signing of the informed consent through 90 (+7) days after the last dose of talimogene laherparepvec or pembrolizumab, or 30 (+7) days following cessation of treatment if the subject initiates new anticancer therapy, whichever is earlier, are recorded in the subject’s medical record and are submitted to Amgen. All serious adverse events must be submitted to Amgen within 24 hours following the investigator’s awareness of the event via the applicable CRF.

If the electronic data capture (EDC) system is unavailable to the site staff to report the serious adverse event, the information is to be reported to Amgen via a paper Serious Adverse Event Contingency Report Form within 24 hours of the investigator’s awareness

of the event. See [Appendix B](#) for a sample of the Serious Adverse Event Worksheet /electronic Serious Adverse Event Contingency Report Form. For EDC studies where the first notification of a Serious Adverse Event is reported to Amgen via the eSerious Adverse Event Contingency Report Form, the data must be entered into the EDC system when the system is again available.

The investigator must assess whether the serious adverse event is possibly related to talimogene laherparepvec or, if applicable, pembrolizumab. This relationship is indicated by a “yes” or “no” response to the question: “Is there a reasonable possibility that the event may have been caused by talimogene laherparepvec”?

The investigator must assess whether the serious adverse event is possibly related to any study-mandated activity or procedure. This relationship is indicated by a “yes” or “no” response to the question: “Is there a reasonable possibility that the event may have been caused by a study activity/procedure”?

The investigator is expected to follow reported serious adverse events until stabilization or reversibility.

New information relating to a previously reported serious adverse event must be submitted to Amgen. All new information for serious adverse events must be sent to Amgen within 24 hours following knowledge of the new information. The investigator may be asked to provide additional follow-up information, which may include a discharge summary or extracts from the medical record. Information provided about the serious adverse event must be consistent with that recorded on the applicable CRF (eg, Events CRF).

If a subject is permanently withdrawn from protocol-required therapies because of a serious adverse event, this information must be submitted to Amgen.

Amgen will report serious adverse events and/or suspected unexpected serious adverse reactions as required to regulatory authorities, investigators/institutions, and IRBs/IECs in compliance with all reporting requirements according to local regulations and Good Clinical Practice (GCP).

The investigator is to notify the appropriate IRB/IEC of serious adverse events occurring at the site and other adverse event reports received from Amgen, in accordance with local procedures and statutes.

9.2.3.1 Follow-up of Adverse Events and Serious Adverse Events

After the initial adverse event/serious adverse event report, the investigator is required to proactively follow each subject at subsequent visits/contacts. All adverse events and serious adverse events will be followed until resolution, stabilization, until the event is otherwise explained, or the subject is lost to follow-up.

All new information for previously reported serious adverse events must be sent to Amgen within 24 hours following awareness of the new information. If specifically requested, the investigator may need to provide additional follow-up information, such as discharge summaries, medical records, or extracts from the medical records. Information provided about the serious adverse event must be consistent with that recorded on the Adverse Events CRF.

9.2.3.2 Reporting Serious Adverse Events After the Protocol-required Reporting Period

There is no requirement to monitor study subjects for serious adverse events following the protocol-required reporting period (as defined in Section 9.1.3) or after the end of study. However, these serious adverse events must be reported to Amgen (regardless of causality) if the investigator becomes aware of them. Per local requirements in some countries (eg, European Union [EU] member states), investigators are required to report serious adverse events that they become aware of after the end of study. If serious adverse events are reported, the investigator is to report them to Amgen within 24 hours following the investigator's awareness of the event.

Serious adverse events reported outside the protocol-required reporting period that occur during the long-term follow-up period until the end of study are to be captured in the Adverse Events CRF, although these events will not be considered treatment-emergent adverse events. Serious adverse events reported outside of the protocol-required reporting period that occur after the end of the study will be captured within the safety database as clinical trial cases for the purposes of expedited reporting.

9.2.3.3 Safety Monitoring Plan

Subject safety will be routinely monitored as defined in Amgen's safety surveillance and signal management processes.

9.2.4 Pembrolizumab Events of Clinical Interest (ECI)

Selected non-serious and serious adverse events known as pembrolizumab ECI must be reported to Amgen within 24 hours.

For the time period beginning when the consent form is signed until enrollment, any ECI, or follow-up to an ECI, that occurs to any subject must be reported within 24 hours to Amgen if it causes the subject to be excluded from the trial, or is the result of a protocol-specified intervention, including but not limited to washout or discontinuation of usual therapy, diet, or a procedure.

For the time period beginning at enrollment through 30 days following cessation of treatment, any ECI, or follow-up to an ECI, whether or not related to pembrolizumab, must be reported within 24 hours to Amgen.

Pembrolizumab ECI for this trial for Group A include:

- an overdose of pembrolizumab, as defined in Section 9.2.6.1
- an elevated AST or ALT lab value that is greater than or equal to 3x the ULN and an elevated TBL lab value that is greater than or equal to 2x the ULN and, at the same time, an ALP lab value that is less than 2x the ULN, as determined by way of protocol-specified laboratory testing or unscheduled laboratory testing.*

*Note: These criteria are based upon available regulatory guidance documents.

The purpose of the criteria is to specify a threshold of abnormal hepatic tests that may require an additional evaluation for an underlying etiology. The trial site guidance for assessment and follow up of these criteria can be found in the Investigator Trial File Binder (or equivalent).

9.2.5 Information Related to Events of Clinical Interest Specifically for Group B HCC Subjects

9.2.5.1 Guidance for Management of Hepatic Events of Clinical Interest

Hepatic ECIs (HECIs) have been described in Section 9.2.6. All of these HECIs will require holding study intervention and notification of the Sponsor within 24 hours. All cases of retreatment after interruption of study intervention for HECl must be reported to the Sponsor and recorded in the database.

Immediate assessment in case of HECl:

All Participants

- All participants should be considered for evaluation according to the directions below within 72 hours of the alert for a non-overdose ECI. For lab assessments of HECIs, central laboratory is preferred; local laboratory is acceptable if central laboratory is not available.
- Procedures:
 - Consider obtaining a consultation with a hepatologist

- Obtain a work-up for hepatitis if there is no underlying hepatitis, including hepatitis A, B, C, D, E, Epstein-Barr virus, and cytomegalovirus
- Assess for ingestion of drugs/supplements with hepatotoxic potential
- Assess for alcohol ingestion
- Assess for potential bacterial infection, biliary obstruction, or occult gastrointestinal bleeding
- Repeat ALT, AST, total bilirubin, direct bilirubin, alkaline phosphatase, γ -glutamyl transpeptidase, INR, and complete blood count with differential
- Measure HCV RNA viral load (applies only for participants who have current active HCV infection or had infection in the past)
- HBV DNA, HBsAg, HBeAg, anti-HBc (total and IgM), anti-HBe, and anti-HBs regardless of prior HBV status (Note: participants should be questioned about compliance with the use of antiviral agents)
- Other laboratories or imaging studies as clinically indicated
- Consider liver biopsy if indicated

HCC patients are at risk for a range of complications that can cause hepatic laboratory abnormalities with or without clinical decompensation. Those with a history of chronic HCV or HBV infection also have the potential to experience virologic flares. Immune-related hepatitis has been observed in approximately 1-2% of participants who received pembrolizumab. The following section provides further guidance on the diagnosis and management of potential hepatic complications among HCC participants in this study. The recommendation is to hold pembrolizumab interventions and initiate per table.

Table 15. Management of Hepatic Events of Clinical Interest for Pembrolizumab:

	Diagnosis	Management
Hepatitis B consider flare or change in HBV immunologic status	Rapid elevation of ALT to > 5 x ULN and/or > 3x baseline	
Interrupt pembrolizumab and talimogene laherparepvec intervention for up to 12 weeks.
 
Start antiviral therapy or check for compliance if HBV is detectable.
 
Measure safety labs for AST, ALT, ALP, T Bili, D Bili, and INR on weekly basis.
 
Measure HBsAg and HBV DNA on weekly basis (if detected at the time of onset of ECI).
 
Evaluate the following every 2-3 weeks: anti-HBe, HBe antigen, anti-HBs, and HBV DNA levels (if not detected at the onset of ECI)
 
Restart pembrolizumab and talimogene laherparepvec intervention only if ALT returns to normal or Grade 1 (if normal at baseline), or to baseline grade (if Grade 2 at baseline) within 12 weeks, and the participant is clinically stable; otherwise, the participant should be permanently discontinued.

Hepatitis C exacerbation in participants with HCV RNA positive	Rapid elevation of ALT to > 5 x ULN and/or > 3x baseline	
Interrupt pembrolizumab and talimogene laherparepvec intervention for up to 12 weeks.
 
Assess use of injection or inhalation drugs.
 
Recheck HCV genotype at the time of relapse of HCV RNA to rule out new infection.

Relapse of HCV infection for participants with successfully treated or new HCV infection	If HCV RNA was TND at baseline, and now has confirmed detectable HCV RNA (2 specimens, 1 week apart)	
Measure safety labs for AST, ALT, ALP, T Bili, D Bili, and INR on weekly basis
 
Measure HCV RNA levels every 2 weeks.
 
Please discuss risk benefit with Sponsor prior to starting HCV antiviral therapy.
 
Restart pembrolizumab and talimogene laherparepvec intervention only if ALT returns to normal or Grade 1 (if normal at baseline), or to baseline grade (if Grade 2 at baseline) within 12 weeks, and the participant is clinically stable; otherwise, the participant should be permanently discontinued.

Immune-related Hepatitis	If any of the HECI criteria is met as defined in the protocol Section 9.2.6	
Interrupt pembrolizumab and talimogene laherparepvec study treatment for up to 12 weeks.
 
Start IV corticosteroid 60 mg/day of prednisone or equivalent followed by oral corticosteroid.
 
Monitor with biweekly laboratory tests, including AST, ALT, T Bili, D Bili, ALP, and INR.

Table 15. Management of Hepatic Events of Clinical Interest for Pembrolizumab:

	Diagnosis	Management
Immune-related Hepatitis (continue)	
Note:
 
Immune-related hepatitis is a diagnosis made after excluding other possible etiologies such as viral flare, biliary or vascular obstruction, infection, medications, and alcohol use usually immune-related hepatitis response to dechallenge and/or steroids and re-occurs with rechallenge
	
Restart pembrolizumab and talimogene laherparepvec intervention only if:
 
 Abnormal laboratory values resolve to Grade ≤ 1 or baseline (if abnormal at baseline) Taper steroid over 28 days Steroid treatment is tapered to prednisone < 10 mg/day or equivalent 
Permanently Discontinue pembrolizumab and talimogene laherparepvec intervention if:
 
 Laboratory abnormalities do not resolve within 3 weeks Steroids cannot be lowered to ≤ 10 mg/day (or prednisone equivalent) within 12 weeks Decompensation to CP-C status
Other Causes	
Rule out infection with blood, urine, and ascites culture – antibiotics should be started if infection is found
 
If total bilirubin is elevated, imaging should be obtained to rule out vascular compromise, biliary obstruction, and/or tumor progression by imaging
 
Ruled out alcohol use and hepatotoxic drugs including herbal and alternative medications
	
Restart pembrolizumab and talimogene laherparepvec only if laboratory values have returned to Grade 1 or baseline (if normal or Grade 1 at start) or to baseline grade within 3 weeks.
 
If biliary obstruction is present, consultation with a gastroenterologist and/or an interventional radiologist should be obtained to see if the obstruction may be relieved.

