- 107 Cohort 3 and 4: sum of tumor diameters from injectable lesions is at least 8 cm (or possibly greater if there are lesions with necrotic cores) and must be eligible to receive > 4 mL of talimogene laherparepvec as defined in Section 6.2.1.1
- 108 Eastern Cooperative Oncology Group (ECOG) performance status of 0 or 1 (see Appendix G)
- 109 Life expectancy approximately 5 months or more
- 110 Adequate organ function determined within 10 days prior to enrollment, defined as follows:
- Hematological (without need for transfusion and or growth factor support within 10 days):
 - ANC $\geq 1500/\text{mm}^3$ ($1.5 \times 10^9/\text{L}$)
 - platelet count $\geq 100\,000/\text{mm}^3$ ($100 \times 10^9/\text{L}$)
 - hemoglobin ≥ 9 g/dL (90 g/L)
 - Renal:
 - serum creatinine $\leq 1.5 \times \text{ULN}$, or 24-hour creatinine clearance ≥ 60 mL/min for subject with creatinine levels $> 1.5 \times \text{ULN}$. (Note: Creatinine clearance need not be determined if the baseline serum creatinine is within normal limits. Creatinine clearance should be calculated per institutional standard).

- Hepatic:
 - serum TBL $\leq 1.5 \times$ ULN
 - AST $\leq 5 \times$ ULN
 - ALT $\leq 5 \times$ ULN
 - Alkaline phosphatase (ALP) $\leq 5 \times$ ULN
- Coagulation:
 - Prothrombin time (PT) or INR $\leq 1.5 \times$ ULN partial thromboplastin time (PTT) or activated PTT (aPTT) $\leq 1.5 \times$ ULN

111 Child-Pugh score of A ([Appendix F](#))

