Dosing should be permanently discontinued if, in the opinion of the investigator, the subject develops clinical evidence of any serious herpes infection (such as HSV hepatitis, encephalitis, or disseminated infection). Systemic anti-herpetic drugs (eg, acyclovir, valacyclovir, or famciclovir) should only be reserved for suspected cases of severe herpetic infection as outlined in the Guidelines for Suspected Serious Herpetic Infections document, but topically administered anti-herpetic drugs may be administered for limited suspected herpetic skin lesions after they are swabbed and tested for talimogene laherparepvec using qPCR.

For Part 1 Group A Cohorts 1-6, Part 1 Group B Cohorts 5 and 6a, and Part 2 Arms I-VI, in subjects with history of HBV and HCV, viral load should be rechecked when ALT or AST are elevated more than twice their baseline value. If reactivation of HBV or HCV is confirmed, discontinuation of talimogene laherparepvec and starting hepatitis antiviral medication should be considered after consultation with the sponsor medical monitor.

For Part 1 Group B Cohort 6b and Part 2 Group B Arm VI subjects with well-controlled viral hepatitis, please see [Table 15](#). Subjects who discontinue talimogene laherparepvec are to continue to return for all other study procedures and

measurements including the 30-day safety follow-up visit (ie, until approximately 30 [+ 7] days after the last dose of study drug) and long term survival follow-up.

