Note: Non-irAE will be managed as appropriate, following clinical practice recommendations.

^a AST/ALT: > 3.0 to 5.0 x ULN if baseline normal; > 3.0 to 5.0 x baseline, if baseline abnormal; bilirubin: > 1.5 to 3.0 x ULN if baseline normal; > 1.5 to 3.0 x baseline if baseline abnormal

^b AST/ALT: > 5.0 to 20.0 x ULN, if baseline normal; > 5.0 to 20.0 x baseline, if baseline abnormal; bilirubin: > 3.0 to 10.0 x ULN if baseline normal; > 3.0 to 10.0 x baseline if baseline abnormal

^c AST/ALT: > 20.0 x ULN, if baseline normal; > 20.0 x baseline, if baseline abnormal; bilirubin: > 10.0 x ULN if baseline normal; > 10.0 x baseline if baseline abnormal

^d The decision to withhold or permanently discontinue pembrolizumab is at the discretion of the investigator or treating physician. If control achieved or ≤ Grade 2, pembrolizumab may be resumed.

^e Events that require discontinuation include but are not limited to: encephalitis and other clinically important irAEs (eg, vasculitis and sclerosing cholangitis).

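### The hepatitis B and C restart rule in Table 15 omits a Grade 1 baseline ALT, so read literally it discontinues an eligible subject whose flare has resolved to that baseline

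*Protocol*

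**What the plan says.** Table 15 in Protocol Section 9.2.5.1 sets out, by cause, how hepatic events are managed in HCC subjects. For hepatitis B and for hepatitis C, both study drugs are interrupted for up to 12 weeks. They restart "only if ALT returns to normal or Grade 1 (if normal at baseline), or to baseline grade (if Grade 2 at baseline", provided this happens within 12 weeks and the subject is clinically stable; "otherwise, the participant should be permanently discontinued". The same sentence serves hepatitis B and hepatitis C.

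The table has two other restart rules. For immune-related hepatitis, values must resolve to Grade 1 or below "or baseline (if abnormal at baseline". For other causes, they must have "returned to Grade 1 or baseline (if normal or Grade 1 at start) or to baseline grade within 3 weeks".

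Two other places bear on who reaches this rule:

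- Criterion 110 in Section 4.1.1 ("Adequate organ function determined within 10 days prior to enrollment, defined as follows") sets the ALT limit at 5x ULN.
- Section 6.2.1.2 gives no restart level of its own for HCC subjects with viral hepatitis. It says "For Part 1 Group B Cohort 6b and Part 2 Group B Arm VI subjects with well-controlled viral hepatitis, please see" Table 15.

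**The concern.** The condition names two baseline states, and its default is permanent discontinuation. An ALT above ULN but below Grade 2 is eligible and belongs to neither state. Such baselines were expected: the synopsis tolerates mildly abnormal liver tests, and Section 9.2.6 has a separate ALT trigger for subjects who start at 2x ULN or more.

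A site that follows the words exactly would stop treatment for good in a subject whose flare has fully resolved to the starting value. A site that reads for intent would restart. The same facts could then lead to opposite decisions about a drug that Section 3.5.1 allows for up to 35 cycles.

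**Working it through.** The plan gives no figure to reproduce here. The check runs the restart sentence through each eligible baseline grade and each level of recovery.

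**Inputs**
- Restart condition and default: Table 15, hepatitis B and C.
- Eligible baselines: criterion 110, ALT up to 5x ULN, hence normal, Grade 1 or Grade 2.
- Grade bands: footnote a of Table 6 opens Grade 2 with "AST/ALT: > 3.0 to 5.0 x ULN if baseline normal". The protocol cites CTCAE 4.03 without reproducing it, so Grade 1 as above 1.0 to 3.0x ULN is inferred.

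**Two ways to parse the sentence.** On the wide reading, the bracket about a normal baseline governs both 'normal' and 'Grade 1'. On the narrow reading it governs only 'Grade 1', so a normal ALT always permits restart.

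**Results** (12-week and stability conditions taken as met; the other-causes rule and the proposed wording read as the stated level or better)

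| Baseline | ALT now | Wide reading | Narrow reading | Other-causes rule | Proposed wording |
|---|---|---|---|---|---|
| Normal | Normal | restart | restart | restart | restart |
| Normal | Grade 1 | restart | restart | restart | restart |
| Normal | Grade 2 | stop | stop | stop | stop |
| Grade 1 | Normal | stop | restart | restart | restart |
| Grade 1 | Grade 1 | **stop** | **stop** | restart | restart |
| Grade 1 | Grade 2 | stop | stop | stop | stop |
| Grade 2 | Normal | unclear* | restart | restart | restart |
| Grade 2 | Grade 1 | unclear* | unclear* | restart | restart |
| Grade 2 | Grade 2 | restart | restart | restart | restart |

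*Stop if 'baseline grade' means exactly that grade; restart if it means that grade or better.

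Grade 1 is the only eligible baseline from which a return to baseline leads to discontinuation, and this is so on both readings.

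**In multiples of ULN.** The highest ALT at which restart is allowed is 3.0 for a normal baseline and 5.0 for a Grade 2 baseline. For a Grade 1 baseline it is 1.0 on the narrow reading, and there is no such level on the wide reading. On the narrow reading a subject with baseline b must fall below that baseline by 1 − 1/b:

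- b = 1.5: 1 − 1/1.5 = 33%
- b = 2.0: 1 − 1/2.0 = 50%
- b = 2.5: 1 − 1/2.5 = 60%
- b = 3.0: 1 − 1/3.0 = 67%

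Take two subjects with ALT now at 2.0x ULN. One started at 0.5x ULN, is at 2.0/0.5 = 4 times baseline, and may restart. The other started at 2.0x ULN, is exactly at baseline, and may not.

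**Comparison.** The proposed wording matches the other-causes rule in all 9 rows, apart from that rule's 3-week window.

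**The case against.** The strongest reply is that this is guidance, written with 'should', and that any investigator would see the intent from the neighbouring rules. Section 9.2.5.1 also requires the sponsor to be told of these hepatic events within 24 hours, and retreatment to be reported. That is probably how most cases would go, and it keeps the severity low. It does not change what the sentence says: it sets an exclusive condition and then a default of discontinuation.

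Sections 6.4.2 and 6.4.3 help in part. Where talimogene laherparepvec was withheld for possible drug-induced liver injury and another cause is found, 6.4.2 accepts recovery to normal or to baseline, and viral hepatitis is a listed alternative cause. Section 6.4.3 gives a medical-monitor route for pembrolizumab when the cause lies elsewhere, but no restart level. Neither overrides Table 15: Section 6.4 itself refers pembrolizumab hepatic events to 9.2.5.1, and Section 6.2.1.2 refers the viral-hepatitis subjects to the table.

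Two stronger readings are tempting and should not be taken.

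- A reader might infer that a Grade 2 baseline subject may restart at the very ALT that bars a Grade 1 baseline subject. That needs 'baseline grade' to mean that grade or better, a leniency withheld from the Grade 1 subject. The safe comparison is each subject at their own baseline grade.
- A reader might infer that a subject with HCV relapse whose ALT never rose also fails the rule, since that trigger is "If HCV RNA was TND at baseline, and now has confirmed detectable HCV RNA (2 specimens, 1 week apart" and needs no ALT change. This depends on the two hepatitis C rows sharing one management cell, which is plausible but cannot be confirmed from the extracted table. The sentence also speaks of ALT returning, which presupposes a rise, and Section 9.2.6 does not list detectable HCV RNA alone as a hepatic event of clinical interest.

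**Conclusion.** The point holds as a minor wording error in a treatment rule. For hepatitis B and C, Table 15 has no restart branch for a Grade 1 baseline ALT, and its literal default is discontinuation at full recovery to that baseline.

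The reach is small: HCC subjects with viral hepatitis and a Grade 1 baseline who are still on treatment. Section 4 states that enrollment has stopped. The documents give no distribution of baseline ALT, so the number affected cannot be computed. No endpoint or design figure is touched.

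A reader might infer that such a subject loses both drugs. After Amendment 6 that is mostly not so. Part 1 gave talimogene laherparepvec only into liver lesions, and those injections have ended, so Part 1 subjects have none left to lose. Part 2 HCC subjects can receive it only in cutaneous, subcutaneous or nodal lesions. Pembrolizumab is the main loss.

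The ULN figures assume that grades are on the ULN scale. Footnote a of Table 6 also gives a band relative to baseline for abnormal baselines, on which a baseline of 2.0x ULN reaches Grade 2 only above 3.0 × 2.0 = 6.0x ULN. The missing branch does not depend on this, since Table 15 itself speaks of a Grade 2 baseline, which has meaning only on the ULN scale. The ceilings do depend on it.

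**What to change.** In both restart sentences (hepatitis B and hepatitis C) write: *only if ALT returns to Grade 1 or better (if normal or Grade 1 at baseline), or to baseline grade or better (if Grade 2 at baseline), within 12 weeks, and the participant is clinically stable*. Leave the hold triggers, Section 9.2.6 and Section 6.4 as they are.

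Adding only 'Grade 1 or' to the second bracket would not be enough. On the wide reading it would still exclude a Grade 1 baseline subject who improves to normal, and it would leave unclear a Grade 2 baseline subject who improves to Grade 1.

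The cost is one reworded condition in two places, by clarification letter or with the next amendment. It needs no new data and does not change when treatment is held. On the ULN scale, a Grade 1 baseline subject could restart at up to 3.0x ULN, the ceiling already allowed from a normal baseline. If the sponsor intends that scale, the letter can say so in the same line.
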